14. PHARMACODYNAMIC PARAMETERS

Pharmacodynamic parameters will be analyzed in the Effectiveness Population. Analyses of PD assessments will focus on WBC α -Gal A enzyme activity and plasma lyso-Gb₃, Urinary and plasma Gb₃, lyso-Gb₃, α -GAL A enzyme activity, and Neutralizing antibodies with ERT.

Data will be summarized using descriptive statistics will be displayed for change from Analysis Start Date (time of diagnosis or treatment start) to e.g. time points such as the date of the first treatment switch, date of the treatment to migalastat or any other time points of interest.

Analysis Methods

Data will be listed. Listings will contain flags indicating therapy change. Spaghetti plots over time for WBC α -Gal A enzyme activity in males and plasma lyso-Gb₃ for individual patients will be produced. Spaghetti plots will indicate what treatment group a patient was on at the time of measurement.

The change from the Analysis Start Date for a parameter will be defined as the difference between that measurement and the measurements at time points such as the date of the first treatment switch, date of the treatment to migalastat or any other time points of interest.

15. SAFETY ANALYSIS

All patients in the Safety Population will be included in all safety summaries. Safety analyses will also be conducted in safety Population.

15.1. Approach to Safety Analyses

As this is an observational study, patients may switch or stop therapies. In the Safety Population, analysis will present results based on the actual exposure, ie, treatment group at the time of the event (migalastat, ERT, or untreated). As patients can stop or switch therapy while enrolled in the study, they might be counted more than once in the analysis.

Serious adverse events will be analysed as described in Section 13 for the composite FACES.

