13.1.1. Cox Proportional Analysis for Fabry-associated Clinical Events

The time to the first event is defined as time from the Analysis Start Date to the first composite FACE (primary interest), and to the first cardiac, cerebrovascular, renal clinical event, or death due to FACEs. For the primary analysis, patients who complete the study without an event, are lost to follow-up, discontinued the study, started dialysis, had a kidney or heart transplant, or after 30 days they changed/switched therapy (migalastat group) or after they start therapy (untreated group) will be censored. Describing effectiveness in migalastat treated population is of the main interest.

Treatment Switch

The primary analysis will address events that occur on therapy from the Analysis Start Date up until 30 days after the patient stops therapy or switches therapy. The events that happen afterwards will be excluded. For the patients untreated at time of diagnosis, the primary analysis will address events from the time of diagnosis until the patient starts a therapy. The events that happen afterwards will be excluded. An additional analysis will be performed:

1. An analysis that will address events that occur on therapy from the time of Analysis Start Date up until the patient stops therapy or patient switches therapy. For the untreated patients, the analysis will address assessments from the time of diagnosis until the patient starts a therapy. The events that happen afterwards will be excluded.

Primary Analysis Method

The ratio of the hazards of treatment groups will be checked to ensure that the hazard ratios are constant over time. Secondly, the assumption that each variable in the model makes a linear contribution will be checked.

The covariates will include:

- sex
- age at the Analysis Start Date as a continuous variable
- eGFR_{CKD-EPI} at the Analysis Start Date as a continuous variable
- LVMi at the Analysis Start Date
- previous history of cardiac, cerebrovascular, and renal clinical events (composite event) as related to Analysis Start Date
- Length of treatment for Fabry disease

If the measurements are not available, measurements prior to and closest to the Analysis Start Date will be used. In case that more than 50% of values are missing for a given covariate, it will be dropped from the analysis.

The estimate of hazard ratio for migalastat-treated/untreated along with the associated 95% CI will be calculated.

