13.3. Secondary Endpoint: Incidence of FACEs

As this is an observational study, patients may switch or stop therapies. If a patient starts dialysis or receives a kidney or heart transplant, the events afterwards will be excluded.

The analysis of the incidence rate (number of patients with at least 1 event per 1000 person-years) will be performed on the Primary and Secondary Effectiveness Populations.

Treatment Switch

The analysis will address events that occur on migalastat or ERT therapy from the Analysis Start Date or switch date up until 30 days after the patient stops therapy or switches therapy. For the patients untreated at enrollment to the study, the analysis will address events from the time of diagnosis until the patient starts a therapy or during periods that they are untreated after a switch.

The second analysis will address events that occur on migalastat or ERT therapy from the Analysis Start Date or switch date. For the patients untreated at enrollment to the study, the analysis will address events from the time of diagnosis until the patient starts a therapy or during periods that they are untreated after a switch.

Analysis Methods

The calculation of the incidence rate (number of events per 1000 person-years) will be performed on the Primary and Secondary Effectiveness Populations.

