15.2. Serious Adverse Events

An adverse event (AE) is any untoward medical occurrence in a patient administered a pharmaceutical product or device that does not necessarily have a causal relation between the product and the event. An AE can therefore be any unfavorable or unintended sign (including abnormal laboratory finding) or symptom temporally associated with a medicinal product, whether or not related to the medicinal product.

For this study, SAEs are of most importance and will be summarized in the analysis. An SAE is any untoward medical occurrence which:

- Results in death
- Is life-threatening
- Requires inpatient hospitalization or prolongs hospitalization
- Results in persistent or permanent disability or incapacitation
- Results in congenital anomaly or birth defect
- Any important medical event that may not be immediately life-threatening or result in death or hospitalization but, based upon appropriate medical judgment, may jeopardize the patient or may require medical or surgical intervention to prevent one of the other outcomes listed in the definition above, will also be reported as an SAE.

In the Safety Population, the following will be summarized for SAE's for each treatment group: migalastat, ERT, untreated at the time of event:

- Reason for seriousness
- Assessment of causality in relation to current treatment (Definite, Probable, Possible, Unlikely, Unrelated, Untreated at time of event)
- Maximal intensity (Mild, Moderate, Severe)
- Outcome (Ongoing, Resolved, Resolved with sequelae, Fatal, Unknown)
- Event associated with underlying illness (Yes/No)
- Action taken (Discontinued Yes/No)

In addition, a data listing will be provided for all SAEs.

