15.5. Extent of Study Drug Exposure

Study treatment exposure will be summarized using the Safety Population.

Analyses for the extent of exposure will focus on the duration of each respective treatment (migalastat, ERT, or untreated). Duration will be defined as:

$$Dur = End\ date\ of\ treatment - start\ date\ of\ treatment + 1$$

Breaks in therapy or discontinuation in exposure as well as switching therapy will be accounted in the calculations. Missing dates will be imputed as described in Section 6.1. Exposure will be calculated after the dates are imputed.

Extent of exposure (in days) will be compared between the treatment groups using the Wilcoxon Rank Sum test. In addition, the number of patients treated at each visit will be presented by treatment group.

Other summaries which will be presented are average dose (mg) per time period (3 months), ongoing status (yes, no, unknown) and primary reason for interruption/discontinuation (adverse drug reaction, lack of efficacy, disease improvement, patient/guardian decision, investigator decision, pregnancy and/or breast feeding).

All exposure parameters will be included in a by-patient listing.

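### SAP 15.1 applies the Section 13 FACE rules to SAEs, so SAE rates can lose events after dialysis or transplant while that person-time stays in the denominator, and two attribution windows conflict

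*SAP*

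**What the plan says.** - **SAP 15.1** gives two instructions. It assigns by exposure: "analysis will present results based on the actual exposure, ie, treatment group at the time of the event". It then adds, without exception: "Serious adverse events will be analysed as described in Section 13 for the composite FACES".
- **SAP 13.3**, on FACE incidence: "If a patient starts dialysis or receives a kidney or heart transplant, the events afterwards will be excluded". 13.2 has the same rule for prevalence.
- **SAP 13.1.1** handles the same point differently. The primary Cox analysis censors patients who are "lost to follow-up, discontinued the study, started dialysis, had a kidney or heart transplant".
- **SAP 13.3** has two windows. The first counts events on migalastat or ERT "from the Analysis Start Date or switch date up until 30 days after the patient stops therapy or switches therapy". The second has no stated tail: "The second analysis will address events that occur on migalastat or ERT therapy from the Analysis Start Date or switch date". Both also count untreated periods that follow a switch.
- **SAP 15.3** bases SAE incidence on actual exposure calculated under 15.5. Its numerator is patients with at least one event, per 1000 person-years.
- **SAP 15.5** runs exposure from start to end of treatment: "Breaks in therapy or discontinuation in exposure as well as switching therapy will be accounted in the calculations". It has no stop at dialysis or transplant.
- **SAP 7.3** also plans a recurrent-event rate for SAEs, as a total count per 1000 person-years.
- **SAP 15.2** summarises SAEs by treatment at the time of event and lists all of them. **15.4** analyses death from any cause from enrolment.

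**The concern.** The Section 13 rules were written for an effectiveness endpoint. Dialysis and transplantation are themselves FACEs (SAP 3.1), so removing what follows can be defended there. Safety has no such reason: SAP 3.2.2 wants all collected adverse events summarised in the final report unless the protocol justifies otherwise, and the protocol's safety sections contain no dialysis or transplant exception.

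If the exclusion reaches the SAE rates, numerator and denominator end at different times and the rate is biased downward in any group that contributes treated or untreated time after dialysis or transplant. Separately, the two attribution rules can place the same SAE in different groups. With about 115 patients in three treatment categories, a few patients can move a rate, so the choice should not be left to the programmer.

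**Working it through.** **1. Where numerator and denominator stop**

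| SAE output | Events after dialysis/transplant, if Section 13 is followed | Person-time after dialysis/transplant |
|---|---|---|
| 15.3 rate (patients with at least one SAE) | Excluded through 13.3 | Kept (15.5) |
| 7.3 recurrent SAE rate | Excluded through 13.3 | Kept (15.5) |
| Cox analysis in the manner of 13.1.1 | Not counted | Not counted (censored) |
| 15.2 summaries and listing | Kept | Not applicable |
| 15.4 overall survival | Deaths kept | Kept |

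The mismatch is confined to the first two rows.

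**2. Event-count rate (7.3)**

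The documents give no SAE rate, exposure total or dialysis/transplant count, so there is no figure to reproduce and the inputs are assumptions. Let f be the share of a group's exposure after dialysis or transplant, and k the ratio of the later SAE rate to the earlier one. With late events removed and exposure kept,

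reported rate / all-SAE rate = (1 − f) / [(1 − f) + f·k]

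| f | k = 1 | k = 3 | k = 5 |
|---|---|---|---|
| 2% | 0.98 | 0.94 | 0.91 |
| 5% | 0.95 | 0.86 | 0.79 |
| 10% | 0.90 | 0.75 | 0.64 |
| 15% | 0.85 | 0.65 | 0.53 |

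Example, all inputs assumed: 400 person-years, 100 SAEs per 1000 person-years before dialysis, f = 5%, k = 3.
- Early events: 0.100 × 380 = 38. Late events: 0.300 × 20 = 6.
- Late events out, all exposure in: 38/400 = 95 per 1000.
- Everything in: 44/400 = 110 per 1000.
- Both cut at dialysis/transplant: 38/380 = 100 per 1000.

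The mismatched rate is lower than either consistent one.

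**3. Patient-count rate (15.3)**

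A patient with an SAE on that treatment before dialysis still counts, so the loss is smaller. Assume 40 patients followed 10 years (400 person-years), m of them starting dialysis at year 5, first-SAE hazard h per year before dialysis and k·h after. Patients counted are:
- no dialysis: (40 − m)(1 − e^(−10h))
- dialysis, late events excluded: m(1 − e^(−5h))
- dialysis, all events: m(1 − e^(−5h − 5kh))

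For m = 6, h = 0.05, k = 3: 34 × 0.3935 = 13.38; 6 × 0.2212 = 1.33; 6 × 0.6321 = 3.79. The reported rate is 14.71/400 = 36.8 per 1000, against 17.17/400 = 42.9, a ratio of 0.86. Here f = 6 × 5/400 = 7.5%, for which the event-count ratio is 0.925/(0.925 + 0.225) = 0.80. Over m = 2 to 6, h = 0.05 to 0.20 and k = 1 or 3, the 15.3 ratio runs from 0.86 to 0.99.

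**4. Attribution**

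Take an SAE 5 days after migalastat is stopped with nothing started. Under 15.1 it is untreated. Under the first 13.3 analysis it falls within migalastat's 30 days and also within an untreated period, so it can count in both. The tail is 30/365.25 = 0.082 person-years per stop or switch, and 15.5 does not add it to the stopped drug's exposure. The second 13.3 analysis states no tail and is close to 15.1, so the conflict lies with the first.

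**The case against.** The best defence is that the specific text governs over the general sentence. 15.2 and 15.3 set their own SAE summaries, numerator and denominator and do not repeat the exclusion, and Section 15 puts all Safety Population patients in all safety summaries. On that reading nothing is excluded. It is a reasonable reading, but the SAP does not say which text prevails, and the Section 15 statement concerns patients, not events. 15.6 shows that the authors foresaw dialysis and transplant patients in the safety analyses, yet for SAEs the only rule on them is the one imported from Section 13.

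A second defence is that a transplant admission may itself be recorded as an SAE, since hospitalisation is a criterion in 15.2. That event is not after the transplant, so the patient would already be in the 15.3 numerator for that treatment. This reduces the loss in 15.3 but does nothing for the recurrent rate.

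A reader might infer more than the documents support:
- *Late SAEs, including fatal ones, vanish from the report.* They stay in the listing and, as written, in the 15.2 summaries; deaths stay in 15.4.
- *Exposure is kept while events are dropped throughout.* The Cox analysis censors both together.
- *The event-count losses describe the 15.3 rate.* That rate counts patients, so those figures overstate its loss.
- *The cross-reference causes SAEs soon after stopping a drug to be coded as untreated for causality.* That follows from 15.2's own scale, which refers to current treatment, and would survive removal of the cross-reference.

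**Conclusion.** The point stands as an unresolved contradiction with a known direction of bias. If 15.1 is followed as worded, the 15.3 and 7.3 SAE rates are too low wherever a group has post-dialysis or post-transplant time with SAEs that would otherwise count. If 15.3 is taken to override 15.1, those rates are unaffected. The conflict between treatment at time of event and the 30-day tail exists regardless of which reading is taken of the exclusion.

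The size cannot be derived from the documents. The ratios shown rest on assumed values of f, k, m and h, and the patient-count ratios also on constant hazards before and after dialysis. The listing, the 15.2 summaries and 15.4 limit the harm, so this is a defect to correct before analysis and not a failure of the safety reporting as a whole.

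**What to change.** In 15.1, replace the blanket cross-reference with a statement that the Section 13 dialysis/transplant exclusion and censoring do not apply to SAEs. All SAEs and all 15.5 exposure are then counted, in 15.3 and in the 7.3 recurrent rate, with SAEs after dialysis or transplant also shown as a separate row.

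Keep the SAP's own rule, treatment at time of event, for the main SAE table. Add one supportive table that attributes SAEs up to 30 days after stop or switch (the 13.3 window) and adds the same 30 days to that treatment's person-time.

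The cost is SAP wording and one extra table. In that table an SAE, and the 30 days of person-time, can appear under two treatments; a footnote should say so.

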15.2. Serious Adverse Events

An adverse event (AE) is any untoward medical occurrence in a patient administered a pharmaceutical product or device that does not necessarily have a causal relation between the product and the event. An AE can therefore be any unfavorable or unintended sign (including abnormal laboratory finding) or symptom temporally associated with a medicinal product, whether or not related to the medicinal product.

For this study, SAEs are of most importance and will be summarized in the analysis. An SAE is any untoward medical occurrence which:

- Results in death
- Is life-threatening
- Requires inpatient hospitalization or prolongs hospitalization
- Results in persistent or permanent disability or incapacitation
- Results in congenital anomaly or birth defect
- Any important medical event that may not be immediately life-threatening or result in death or hospitalization but, based upon appropriate medical judgment, may jeopardize the patient or may require medical or surgical intervention to prevent one of the other outcomes listed in the definition above, will also be reported as an SAE.

In the Safety Population, the following will be summarized for SAE's for each treatment group: migalastat, ERT, untreated at the time of event:

- Reason for seriousness
- Assessment of causality in relation to current treatment (Definite, Probable, Possible, Unlikely, Unrelated, Untreated at time of event)
- Maximal intensity (Mild, Moderate, Severe)
- Outcome (Ongoing, Resolved, Resolved with sequelae, Fatal, Unknown)
- Event associated with underlying illness (Yes/No)
- Action taken (Discontinued Yes/No)

In addition, a data listing will be provided for all SAEs.

15.3. Incidence of SAEs

Incidence of SAEs is based on actual exposure. The exposure is calculated as per Section [15.5](#). The analysis of the incidence rate (number of patients with at least 1 event per 1000 person-years) will be performed.

15.4. Overall Survival

To assess the overall survival among all patients, a Cox proportional hazards model will be used, provided that the assumptions of Cox proportional hazard are met. The ratio of the hazards of treatment groups will be checked to ensure that the hazard ratios are constant over time. Secondly, the assumption that each variable in the model makes a linear contribution will be checked. Otherwise, Kaplan-Meier log-rank test will be used for this analysis.

Overall survival is defined as time from enrollment into the study until death due to any cause (event).

Covariates will include:

- sex
- enrollment age as a continuous variable
- enrollment eGFR as a continuous variable
- LVMi at enrollment
- time on treatment (ERT or migalastat overall)
- history of cardiac, cerebrovascular, and renal clinical events (a binary endpoint based on the composite event) prior to enrollment
- length of therapy for Fabry disease

If the measurements are not available, measurements prior to and closest to the Analysis Start Date will be used. In case that more than 50% of values are missing for a given covariate, it will be dropped from the analysis.

In the Safety Population where patients are analyzed based on the actual exposure, a Cox model run similarly to the analysis in Section [13.1.2](#) will be used but with 3 time-dependent variables indicating whether or not a patient is on migalastat, ERT, or untreated at time t. A patient may be in 1 or more treatment groups and a patient may be both left and right censored. For example, a patient that begins migalastat, stops at Month 3, begins ERT at Month 6, and then dies at Month 9 will be represented 3 times in the design matrix; the first for migalastat being right censored at Month 3, the second being for ERT left censored at Month 3 and right censored at Month 6, and finally, for untreated, being right censored at Month 6 and having an event at Month 9.

The estimate of hazard ratio for migalastat/ERT and migalastat/untreated along with the associated 95% CI will be calculated.

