4.1. Randomization

Not applicable for this study.

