A sensitivity analyses will be done using Kaplan-Meier approach (log-rank test).

The analysis between migalastat and ERT will be performed like the analysis above for the comparison between migalastat treated and untreated patients. The origination of analysis will be start of treatment.

Because patients could switch treatment many times during the 20-year period, the time to the first event within each treatment period will be calculated from each switch date and descriptive statistics will be presented. Please note that each patient could be counted more than once in this analysis. Two options will be used for these analyses. The first analysis will address events that occur on therapy from the Analysis Start Date up until 30 days after the patient stops therapy or from the switch date to the date of a subsequent switch or stopping therapy. The second analysis will address events that occur on therapy from the Analysis Start Date up until the patient stops therapy or switches therapy or from the switch date to the date of a subsequent switch or stopping therapy.

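### SAP 15.4 drops all covariate adjustment of overall survival if a Cox assumption fails, and the primary endpoint's log-rank sensitivity analysis omits the same confounders

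*SAP*

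**What the plan says.** **Overall survival (SAP 15.4).** The main analysis is conditional: "a Cox proportional hazards model will be used, provided that the assumptions of Cox proportional hazard are met". There are two checks. The first is "The ratio of the hazards of treatment groups will be checked to ensure that the hazard ratios are constant over time". The second is that "the assumption that each variable in the model makes a linear contribution will be checked". Neither has a stated test or threshold. The action on failure is one sentence: "Otherwise, Kaplan-Meier log-rank test will be used for this analysis". The covariates are sex, age, eGFR, LVMi, time on treatment, length of therapy and "history of cardiac, cerebrovascular, and renal clinical events (a binary endpoint based on the composite event) prior to enrollment". The same section then plans a second Cox model, with time-dependent treatment by actual exposure. No separate fallback is given for it, and its covariates are not restated.

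**Primary endpoint (SAP 13.1.1).** The same two checks are made, with no action stated if they fail. The adjusted migalastat/untreated hazard ratio is to be reported unconditionally. Then: "A sensitivity analyses will be done using Kaplan-Meier approach (log-rank test"). Again no strata or covariates are named.

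**Allocation (SAP 4.1).** Randomisation: "Not applicable for this study".

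**The concern.** Adjustment is the main protection an observational treatment comparison has, and the SAP recognises this by listing confounders. The 15.4 rule removes all of them at once, and a defect in a single covariate is enough to trigger it. What is then tested is a crude contrast. If treated and untreated patients differ in sex, age or organ involvement, a small p-value could come from those differences alone.

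Imbalance is plausible from the protocol's own background section. It describes classical males as bound to progress to multiorgan failure if untreated, and penetrance in heterozygous females as incomplete. Sex and phenotype may therefore influence both who is treated and who has events.

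The remedy also fits neither problem. Non-linearity is a question of functional form, which a flexible or categorised term resolves within the model. Non-proportional hazards are a setting in which the log-rank test itself loses power.

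**Working it through.** The documents give no event count, effect size or power calculation, so there is no figure to reproduce. The check is a reading of the text followed by an illustration.

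**1. Is adjustment attached to either log-rank test anywhere?**
- SAP 15.4 and 13.1.1: none named.
- Protocol, Descriptive statistics: a general statement about stratifying by sex, age and other factors, not linked to a log-rank test and not carried into the SAP.
- SAP 12: subgroup analyses in subsets, some descriptive only. These are not an adjusted overall comparison.

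Both tests are therefore unadjusted as written.

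**2. How easily could the 15.4 rule fire?** Five of the seven covariates are naturally continuous: age, eGFR, LVMi, time on treatment and length of therapy. Suppose each were tested for linearity at 5%, independently (an assumption, since the SAP gives no criterion). At least one would then fail by chance with probability 1 − 0.95^5 = 0.226, or about 23%, in a model that is in fact linear.

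**3. Sex imbalance alone, no drug effect.** From the SAP: N = 115, one third male, two-sided 0.05. Assumed: two equal groups, exponential hazards, uniform 2 to 20 year censoring, male hazard ratio 2 or 3, baseline hazard 0.01 or 0.03 per year (about 15 to 44 events), 4,000 runs per scenario. Ranges cover these four settings.

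| Male, treated v untreated | Unadjusted log-rank rejects | Log-rank stratified by sex rejects |
|---|---|---|
| 33% v 33% | 4.8–5.4% | 4.6–5.5% |
| 40% v 27% | 5.0–7.2% | 4.4–5.1% |
| 50% v 17% | 8.1–23.0% | 4.9–5.1% |
| 60% v 7% | 11.6–51.5% | 4.6–5.6% |

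The simulation standard error at 5% is √(0.05 × 0.95 / 4000) = 0.34 percentage points.

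*Analytic cross-check.* Crude HR ≈ (1 + (HR_male − 1)p_treated) / (1 + (HR_male − 1)p_untreated). For 50% v 17% male:
- HR_male 2: 1.5 / 1.167 = 1.29
- HR_male 3: 2 / 1.334 = 1.50

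Rejection ≈ Φ(√(D/4) × |ln HR| − 1.96), with D the number of events. For HR 1.50 and D = 30 this is Φ(2.739 × 0.405 − 1.96) = Φ(−0.85), about 20%. From HR 1.29 with 15 events to HR 1.50 with 50 events the range is about 7% to 30%, in line with the table.

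**4. Sex and age imbalance together, no drug effect.** Assumed: N = 115, 45% treated, mean age 40, SD 14 to 15, the same censoring, about 7 to 50 events.

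| Imbalance | Assumed male HR; HR per decade | Unadjusted log-rank rejects |
|---|---|---|
| 50% v 25% male, 5 years older | 1.5; 1.3 | at most about 10%; no clear inflation at about 7 events |
| 50% v 20% male, 10 years older | 2; 1.5 | 14–47% |
| 60% v 15% male, 14 years older | 2; 1.6 | 37–84% |

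A Cox model with treatment, sex and age rejects in 4–6% of runs at about 16 to 50 events.

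**5. What this does and does not show.** The simulated data have proportional hazards and log-linear covariates, so the 15.4 fallback would fire on them only by false alarm. The figures describe an unadjusted log-rank test in a confounded comparison. They do not describe the check-then-switch rule or the planned seven-covariate, three-group analysis.

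**The case against.** **The primary analysis is untouched.** A reader might infer that the primary endpoint also loses its adjusted model. It does not: 13.1.1 reports the adjusted hazard ratio without condition, 13.1.2 adds a time-dependent Cox analysis, and the log-rank test is an addition. The replacement concerns one safety endpoint. This stands.

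**The log-rank test would not be the only survival comparison.** The exposure-based Cox model in 15.4 has no stated fallback. This stands in part: its covariates are not restated, so it is not clear that it supplies the missing adjustment.

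**The inflation is assumed.** A reader might take a figure such as 52% or 84% as the false-positive rate of this study. The documents give neither the imbalance nor the number of deaths, and with similar groups the inflation is negligible. This stands as to size. The direction does not depend on it.

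**A Cox/log-rank disagreement need not mean confounding.** This also stands. The protocol bars imputation, and the SAP drops a covariate only above 50% missing, so the Cox model may use fewer patients than the log-rank test. Selection, non-proportionality and non-collapsibility could each produce a discrepancy. Because disagreement has several possible explanations, and agreement may be coincidental, the log-rank test is a poor robustness check.

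**An elaborate remedy is out of proportion.** Weighted curves, splines and restricted means together are more than about 115 patients with an unknown number of deaths clearly support. This is accepted, and the fix is kept simple.

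**Conclusion.** The point holds for overall survival. Under 15.4, failure of proportional hazards or of linearity in any one covariate replaces an adjusted comparison with an unadjusted test, in a study without randomisation, although either failure can be handled with adjustment kept. For the primary endpoint the narrower point holds: the adjusted model remains, but its named sensitivity analysis omits the same confounders and so does not test the robustness of the adjusted result. In addition, 13.1.1 leaves open what happens if its checks fail.

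The textual part rests on the SAP alone. The size of the bias cannot be derived from the documents; it runs from negligible to large according to assumed imbalance, covariate effects and event counts. The SAP should be changed, but the primary analysis is not invalidated.

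**What to change.** In SAP 15.4, replace the fallback sentence with wording such as: *The analysis will remain adjusted. A covariate that violates proportional hazards will be used as a stratification factor; a non-linear covariate will be categorised or modelled flexibly; if the treatment effect is not proportional, period-specific adjusted hazard ratios will be reported as far as event numbers allow.*

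State the same action in 13.1.1, and in both sections name the test or graphical criterion for each check in advance.

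Make the log-rank sensitivity analysis in 13.1.1 stratified, at least by sex and age group, or weighted. Label the unadjusted Kaplan-Meier curves as descriptive.

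The cost is SAP wording and slightly more programming, with no new data. Stratifying with few events loses some precision, and period-specific estimates may not be feasible if deaths are rare.
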